2. STUDY OBJECTIVES

2.1 Primary Objectives

To determine the safety and efficacy of dexamethasone insert at Day 28 and Day 42 respectively, as measured by –

- Improvement in the corneal fluorescein staining in the treatment arm versus the sham arm
- Improvement in most bothersome dry eye symptoms ((1) eye dryness, or (2) eye fatigue, or (3) eye discomfort) as measured using VAS (0 to 100) in the treatment arm versus sham arm
- We also will determine efficacy of the treatment by determining the responder rate in the treatment versus sham arm.
-
- 1- One full severity grade improvement in corneal staining. The percentage of subjects achieving 1 severity grade improvement in corneal staining (responders) in the treated arm versus sham arm will be compared statistically
- 2- 30% improvement in the most bothersome symptom (responders). The percentage of subjects achieving a 30% improvement in their most bothersome symptom in the treated arm versus the sham arm will be compared statistically.

2.2 Secondary Objectives

To determine the safety of dexamethasone insert through Day 42, as measured by –

- Intraocular pressure monitoring
- Cataract formation or worsening of existing cataract as determined by slit-lamp examination and best spectacle corrected visual acuity.
- Other adverse events (unsolicited, but volunteered by the subjects)

3. STUDY DESIGN

3.1 Study Description and Duration

This prospective, double-masked, randomized, sham-controlled, single-center, phase IV investigator-sponsored clinical study seeks to investigate the safety and efficacy of dexamethasone 0.4 mg lacrimal insert over a 42 day period.

4. SELECTION, WITHDRAWAL, AND REPLACEMENT OF PATIENTS

4.1 Study Population

The study aims to enroll 85 Patients (170 eyes) with dry eye syndrome (DES) or keratoconjunctivitis sicca (KCS), requiring topical steroid treatment.

4.1.1 Inclusion Criteria

A patient's study eye must meet the following criteria to be eligible for inclusion in the study:

- 1) Male or Female Age 18-100
- 2) Capacity to give informed consent
- 3) Ability to follow study direction and complete all study visits
- 4) A previous or current diagnosis of dry eye by an eye care specialist, whereas treatment is requiring the use of a topical steroid
- 5) Able to have a lacrimal plug placement into both lower puncta. If lower puncta are already plugged or cauterized/sealed, upper puncta will be used

- 6) Females of childbearing potential unwilling to use reliable form(s) of birth control throughout study period
- 7) Clinical diagnosis of dry eye syndrome (DES) or keratoconjunctivitis sicca (KCS), in which the following has been bilaterally documented in the ophthalmic and medical histories:
 - i. history/diagnosis of dry eye
 - ii. has taken or is on prescription drops (including but not limited to topical steroids, cyclosporine or lifitigrast)
- 8) Presence of all of the following in both eyes at Baseline (Day 1):
 - i. Total OSS of 3 or more with at least 2+ corneal staining (0-6)
 - ii. Unaesthetized Schirmer level of <10 mm at 5 minutes
 - iii. Presence of significant symptoms defined as 30mm or higher score of (1) eye dryness, or (2) eye fatigue, or (3) eye discomfort as measured using VAS, in both eyes.

At the baseline visit, the most bothersome symptom (of the three) will be determined and used as the main symptom outcome measure throughout the study.

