1.2 Rationale

Previous studies showed that dexamethasone and loteprednol topical drops have led to favorable results (4-7). However, the requirement of frequent instillation of drops by the patients is problematic causing discomfort and blurring of vision and requires remembering and dexterity for instillation, poor compliance is not uncommon (7). In addition we believe that instillation of drops disturbs the homeostasis of the natural tear film due to physical and chemical trauma due to large drop volume (50 microliters) hammering on the eye surface (which can only hold 7 to 10 microliters). Particularly washing away of the mucin layer that holds all the “good ingredients” in the tears is harmful to the ocular surface. Therefore, “dropless” treatment of dry eye is desirable.

Dextenza® (dexamethasone ophthalmic insert, Ocular Therapeutix Inc., Bedford, MA) is a corticosteroid intracanalicular insert approved by US-FDA in November 2018 for the treatment of post-surgical ocular inflammation and pain. It is inserted into the lower lacrimal punctum and into the canaliculus. A single insert releases a 0.4 mg dose of dexamethasone for up to 30 days following insertion. Dextenza® is resorbable and does not require removal. We hypothesize that Dextenza® could mimic short-term topical steroid use in a tapering manner in patients with clinically significant dry eye and show efficacy in improving its symptoms and signs, as was previously shown with other steroid preparations. If proven, the use of Dextenza® may shift paradigms in the management of the clinically significant ocular surface disease. To test this hypothesis, we propose to study the effects of Dextenza® in the treatment of clinically significant dry eye. This proposal has several strengths over a non-masked protocol:

- 1- We have identified a tear duct plug with a comparable size (size 0.5mm) that lasts 60-180 days (Vera90TM). This would serve as an excellent comparison to Dextenza and allow the study to be a double-masked design. Both devices are not visible at the slit-lamp once inserted.
- 2- The investigator enrolling the patient (inserting the study treatment versus the control treatment) will be different than the examining investigator for each patient to allow the study to be truly double masked.
- 3- Because each patient will have one Dextenza eye and one control eye, the efficacy and safety of the treatment will be fairly, effectively, and accurately assessed. The

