4.1.2 Exclusion Criteria

A patient who meets any of the following criteria will be excluded from the study:

- 1) Use of Contact lenses within 1 week of screening visit or during the study
- 2) Any ocular surgery (including tear duct cauterization) within the 3 months
- 3) Inability to place a lacrimal device into upper or lower puncta of both eyes (if upper in R eye should be upper in the left eye and vice versa)
- 4) Inability to participate in the wash out period
- 5) Use of topical glaucoma medications (With exception of rescue medication)
- 6) Pregnancy, nursing or intention of pregnancy or nursing in the study period.
- 7) Monocular patients
- 8) Uncontrolled systemic disease (defined as frequent or recent change in the medication regimen)
- 9) Patients who are currently on with stable doses of oral steroids, topical cyclosporine or lifitigrast, topical tacrolimus or pimecrolimus are eligible as long as there has been no change in the dose in the last 3 months
- 10) Patients who are on topical steroids (with the exception of rescue medication)
Patients who have used steroids recently but have been off for at least 2 weeks will be eligible.
- 11) Current enrollment in any other investigational drug or device study or participation of study within 30 days of baseline visit.
- 12) Known allergy or sensitivity to any of the clinical or experimental drugs used in this study including history of steroid response.

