- c. Patients who had endothelial corneal transplantation are eligible as long as the surgery was 3 months or longer ago

v. History of other inflammatory or autoimmune medical disease (GVHD, RA, SLE, etc), in particular presence of SS (primary or secondary), and related symptoms.

- a. These patients are eligible as long as they do not have cicatrizing conjunctivitis (such as SJS, MMP, etc)

2. Informed consent

Informed consent will be given to the patient to review at the time of approach in the clinical setting, or sent to the patient's home if identified via chart review. The patient will be given ample time to review the consent form, and will return on the day of the study visit with any questions. All questions will be answered and a discussion will be had with the person obtaining consent prior to the consent form being signed.

3. Pregnancy test

A standard urine pregnancy test provided by Ocular Therapeutix will be performed on women of childbearing potential at Baseline and Exit visit. A positive test will exclude patient from enrollment into the study as well as will be considered a serious adverse event if occurred during the study period.

4. Dry eye symptoms as measured using Visual Analog Scale (VAS).

Patients will complete VAS questionnaires for each eye in regard to eye dryness, eye discomfort, and eye fatigue. The most bothersome symptoms will be determined (of the three symptoms) at baseline and used throughout the study as the main symptom.

Patients will be given the questionnaire and expected to complete on their own. Help may be given to patients who have difficulty reading or understanding of the definition of the questions which will accompany the three questions.

The patient marks on the line the point that they feel represents their perception of their current state at each visit.

The VAS score is determined by measuring in millimeters using a ruler from the left hand end of the line (0) to the point that the patient marks, to a maximum 100.

5. Visual acuity (VA)

Distance visual acuity will be measured under monocular conditions using the subjects' habitual correction for distance (if wearing). The Snellen Chart will be used. If less than 20/20, pt will have Best Spectacle Corrected Visual Acuity (BSCVA) measured via Manifest Refraction.

6. Schirmer's test without anesthesia.

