5.1.1 Study Procedures

Patients will be instructed not to instill any eye drops one hour prior to any study visit.

SCREENING VISIT/RUN IN (Day -14 to -7) – Either Examining or Treating physician will perform.

The following information will be collected:

- Informed Consent
- Inclusion/exclusion
- Demographics
- Medical history and concurrent illnesses
- Concomitant medications
- Log/Dispense Rescue medications
- Ocular Surface Disease Index Questionnaire (OSDI)
- Schirmer test without anesthesia
- OSS (Corneal and conjunctival)
- Intraocular Pressure (IOP)
- Slit Lamp Examination (SLE)
- Dilated Fundus Exam (DFE)
- Rescue Med Recording

BASELINE VISIT (Day 1)- Treating Physician (Unmasked)

If run-in Visit was NOT performed:

- Informed Consent
- Inclusion/Exclusion
- Demographics

- Medical History and concurrent illnesses
- Dilated Fundus Exam (DFE)

Needed for all Baseline Day 1:

- Concomitant medications
- Urine Pregnancy Test
- Log/Dispense Rescue Meds
- Insert Study Drug/Control
- Best Corrected Spectacle Visual Acuity (BSCVA)
- VAS
- Schirmer without anesthesia
- OSS
- IOP
- SLE
- AE recording

VISIT 2 (14+/-3 days) – Examining Physician (Masked)

- Concomitant medications
- Log/Dispense Rescue Meds
- OSS
- IOP
- SLE
- Rescue med recording
- AE recording

VISIT 3 (28+/-3 days) – Examining physician (Masked)

- Concomitant medications
- Log/Dispense Rescue Meds
- VAS
- OSS
- IOP
- SLE
- Rescue med recording
- AE recording

VISIT 4 (42+/-3 days) – Examining Physician

- Concomitant Medications
- Log/Dispense Rescue Meds
- Pregnancy Test
- BSCVA
- VAS

- Schirmer W/O anesthesia
- OSS
- IOP
- SLE
- Dilated Fundus Exam
- Rescue med recording
- AE recording

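### Inclusion criterion 6 is inverted: as written, the protocol's only contraception rule is met by the women it is evidently meant to screen out

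*Combined protocol and SAP*

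**What the plan says.** The opening line of Section 4.1.1 says that a patient's "study eye must meet the following criteria to be eligible for inclusion in the study". Eight numbered items follow. Item 1 is "Male or Female Age 18-100". Item 6 is "Females of childbearing potential unwilling to use reliable form(s) of birth control throughout study period".

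Two other parts of the protocol bear on pregnancy:

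- **Section 4.1.2, item 6** excludes patients for "Pregnancy, nursing or intention of pregnancy or nursing in the study period". It does not mention birth control.
- **Section 5.1, item 3** provides a urine pregnancy test that "will be performed on women of childbearing potential at Baseline and Exit visit". It continues: "A positive test will exclude patient from enrollment into the study as well as will be considered a serious adverse event", the latter if the pregnancy occurs during the study.

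Table 1 and Section 5.1.1 place the tests at Day 1 and at Visit 4 (Day 42, plus or minus 3 days). Table 1 adds one at early termination. None is scheduled at Day 14 or Day 28.

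On exposure, Section 1.2 states: "A single insert releases a 0.4 mg dose of dexamethasone for up to 30 days following insertion".

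**The concern.** An inclusion list is a set of conditions that must all hold. Item 6 instead describes a group that a trial with a pregnancy exclusion would be expected to keep out. Either the item sits in the wrong list or the word *unwilling* has the wrong sign. On either explanation, the criterion as written says the opposite of what is evidently meant.

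What is at stake is participant protection and a clean eligibility record. The protocol itself treats a pregnancy during the study as a serious adverse event, so it regards this as a safety matter. If staff apply the text, they admit the wrong women and bar all men. If they silently apply the opposite, every man and every willing woman enrolled fails a written criterion, and the approved protocol does not describe actual practice. A woman who declines contraception could also be enrolled without breaching any written rule.

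**Working it through.** This is a check of wording and logic. The plan gives no figure to reproduce.

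**Step 1. Apply the written items to each type of patient.** Inclusion 1 and inclusion 6 must be met, and exclusion 6 must not be triggered. Women described as not intending pregnancy are also taken to be neither pregnant nor nursing. The last column shows the result if item 6 were moved unchanged to the exclusion list.

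| Patient | Inclusion 1 | Inclusion 6 as written | Exclusion 6 | Result as written | Result if item 6 is an exclusion |
|---|---|---|---|---|---|
| Man | met | not met | not triggered | barred | may enter |
| Woman not of childbearing potential | met | not met | not triggered | barred | may enter |
| Woman of childbearing potential, willing to use birth control, not intending pregnancy | met | not met | not triggered | barred | may enter |
| Woman of childbearing potential, unwilling, not intending pregnancy | met | met | not triggered | may enter | barred |
| Woman of childbearing potential, unwilling, intending pregnancy | met | met | triggered | barred | barred |

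As written, these items admit only the fourth group. That cannot be the intention, because inclusion 1 opens the trial to both sexes. With the same words in the exclusion list, the first four results reverse and the conflict with inclusion 1 disappears.

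**Step 2. Look for another contraception rule.** The available text mentions birth control nowhere else. Exclusion 6 turns on being pregnant or nursing, or intending either. Unwillingness to use contraception is a different condition, so the fourth group passes exclusion 6. The pregnancy tests detect a pregnancy but set no entry condition on contraception.

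**Step 3. Place the tests against the exposure period.** Inputs: insertion on Day 1 (Table 1), release for up to 30 days (Section 1.2), and exit at Day 42 plus or minus 3 (Section 5.1.1).

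- End of the stated maximum release: 1 + 30 = about Day 31.
- Exit test window: 42 − 3 = Day 39 to 42 + 3 = Day 45.
- Interval between the two tests: 42 − 1 = 41 days (39 − 1 = 38 to 45 − 1 = 44).
- Exit test minus end of release: 42 − 31 = 11 days (39 − 31 = 8 to 45 − 31 = 14).

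In a patient who completes the study, a pregnancy beginning after Day 1 would therefore meet its next scheduled test only after the stated release period has ended. These intervals describe the test schedule, and correcting item 6 would not change them. They show only why the tests cannot stand in for an entry rule.

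**The case against.** The strongest reply is that the slip gives itself away. No screener could run the trial on a reading that bars every man, so staff at this single site will apply the intended rule. Other safeguards also remain:

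- Exclusion 6 and the Day 1 test keep out women who are pregnant, or who intend to be, at the time of insertion.
- After insertion, Section 5.2.2 has patients asked whether their medical or ocular history has changed. Adverse events are recorded at Days 14 and 28, and Section 5.1.2 allows unscheduled visits for any reason.
- The risks listed in Section 4.4 are eye pressure, infection and healing. Fetal harm is not among them.

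Much of this stands. The error is likely to be noticed, the gap is narrow, and the documents give no basis for calling the consequence large. It would also overstate matters to say that nothing protects women of childbearing potential.

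It does not remove the point. The routes available between the two tests depend on the patient knowing of a pregnancy and reporting it. They detect pregnancy after exposure and do not screen at entry. Reliance on staff to reverse the written criterion is itself a departure from the protocol. The woman who declines contraception, does not intend pregnancy and tests negative on Day 1 still meets every written rule on this subject.

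**Conclusion.** The concern holds. Inclusion 6 is wrong as written and contradicts inclusion 1, and no other available text supplies the missing contraception rule. It should be corrected, although it does not threaten the trial's results: 1 of 8 inclusion items is affected, and no sample size, power, alpha or efficacy figure changes.

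The conclusion carries three limits:

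- Consent pages are not part of the text reviewed, so the statement that this is the only contraception rule applies to the protocol text alone. A consent form would not in any case correct the criterion.
- The documents do not say how many of the 85 patients are women of childbearing potential, so the number exposed to the gap cannot be estimated.
- The safety relevance rests on the protocol's own exclusion of pregnancy and its classing of pregnancy on study as a serious adverse event, not on any outside estimate of risk.

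**What to change.** The sponsor-investigator should state the intended rule and reconcile inclusion 6 with the opening line of Section 4.1.1, inclusion 1, exclusion 6 and the pregnancy-test text in Section 5.1, item 3. One way is to move item 6, as worded, to Section 4.1.2. Merely replacing *unwilling* with *willing* in the inclusion list would still bar men and women not of childbearing potential if read literally. Any screening checklist should be updated to match.

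The same amendment can tidy exclusion 9. It sits in the exclusion list but says which patients on stable treatment may enter. Its content agrees with Section 5.1, items 1.ii.a and 1.ii.d, so it needs only to be recast as an exclusion consistent with its own 3-month condition.

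The cost is one line of protocol text for item 6, one line for exclusion 9, a checklist update, and the IRB review that Section 7.4 requires for any amendment. The statistical analysis does not change.

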4.1.2 Exclusion Criteria

A patient who meets any of the following criteria will be excluded from the study:

- 1) Use of Contact lenses within 1 week of screening visit or during the study
- 2) Any ocular surgery (including tear duct cauterization) within the 3 months
- 3) Inability to place a lacrimal device into upper or lower puncta of both eyes (if upper in R eye should be upper in the left eye and vice versa)
- 4) Inability to participate in the wash out period
- 5) Use of topical glaucoma medications (With exception of rescue medication)
- 6) Pregnancy, nursing or intention of pregnancy or nursing in the study period.
- 7) Monocular patients
- 8) Uncontrolled systemic disease (defined as frequent or recent change in the medication regimen)
- 9) Patients who are currently on with stable doses of oral steroids, topical cyclosporine or lifitigrast, topical tacrolimus or pimecrolimus are eligible as long as there has been no change in the dose in the last 3 months
- 10) Patients who are on topical steroids (with the exception of rescue medication)
Patients who have used steroids recently but have been off for at least 2 weeks will be eligible.
- 11) Current enrollment in any other investigational drug or device study or participation of study within 30 days of baseline visit.
- 12) Known allergy or sensitivity to any of the clinical or experimental drugs used in this study including history of steroid response.

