DOSE/ROUTE/SCHEDULE:	Each patient's right eye will be randomized to receive either the treatment or the control. The left eye will automatically receive the alternative. For example if the right eye of the patient gets randomized to receive the study medication, left eye will automatically be the control eye. If the right eye gets randomized to receive the control treatment, the left eye will receive the study medication.
	Control eye will receive a sham treatment: commercially available tear duct plug without the dexamethasone (Vera90TM EXTENDED WEAR SYNTHETIC ABSORBABLE PUNCTAL PLUG made of E-Caprolactone-L-Lactide copolymer (PCL). Absorbs in 60 to 180 days. Size 0.5mm which is comparable to the study treatment)
	RESCUE MEDICINE: In patients with worsening of signs or symptoms, topical loteprednol 0.5% (Lotemax) drops up to 4 times a day, mimicking the usual practice, can be used at the discretion of the principle investigator.
	In patients with increased intraocular pressure (more than 5 points greater than baseline or more than 5 points higher than the fellow eye) treatment with topical beta blocker/betaxolol 0.5% (Betoptic) drops can be used 2 times a day to bring down the pressure at the discretion of the principle investigator.

Endpoint(s)

PRIMARY EFFICACY: Efficacy will be measured at 28 days.)

We have two co-primary end points:

- 1- Dry eye Sign: Corneal staining score measured using OSS scale on Day 28. The difference between the average corneal staining in the treated arm versus the average corneal staining in the sham arm will be compared statistically.
- 2- Patient reported symptom: Most bothersome symptom (any one of the (1)eye dryness, (2)eye discomfort, or (3)eye fatigue will be established as the most bothersome symptom at baseline for each eye) measured using visual analogue scale (0 to 100). The difference between the average most bothersome symptom in the treated arm versus the average most bothersome symptom in the sham arm will be compared statistically.

Secondary Efficacy:

We have two secondary end points:

- 1- Corneal staining responder analysis. Responder is defined as one full severity grade improvement in corneal staining. The percentage of subjects achieving 1 severity grade improvement in corneal staining (responders) in the treated arm versus sham arm will be compared statistically.

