5. STUDY SCHEDULE OF EVENTS AND VISIT DESCRIPTIONS

5.1 Schedule of Events

Study assessments and procedures are presented by visit in Table 1

Table 1 Schedule of Events

Procedure	Run In* (Day -14 to -7)	Visit 1* (Day 1)	Visit 2 (Day 14)	Visit 3 (Day 28)	Visit 4 (Day 42)	Early Termination
Informed Consent	X	X**				
Inclusion/Exclusion/Demographics	X	X**				
Medical history and concurrent illnesses	X	X**				
Concomitant medications	X	X	X	X	X	X
Pregnancy Test		X			X	X
Log/Dispense Rescue Meds	X	X	X	X	X	
Insert Study Drug/Control		X				
BSCVA		X			X	X
VAS	X	X		X	X	X
Schirmer (W/O anesthesia)	X	X			X	X
OSS (corneal and conjunctival)	X	X	X	X	X	X
IOP	X	X	X	X	X	X
SLE	X	X	X	X	X	X
Dilated Fundus Exam	X	X**			X	X
Rescue med recording	X		X	X	X	X
AE recording		X	X	X	X	X

*If no run-in required, patient will start at baseline visit/ Day 1

**Required in absence of run-in visit

After having obtained an informed consent patients will be assigned a unique patient number and undergo the below procedures in the order they are listed.

1. Medical History and Review of Systems
 - i. Contact lens and glasses wearing (contact lens wear has to be discontinued 1 week prior and for the duration of the study)
 - ii. Current eye drops used:
 - a. Patients who are on dry eye drops, such as artificial tears, cyclosporine, or lifitigrast treatment will be eligible as long as the doses have been stable for at least 3 months
 - b. Patients who are on steroid drops will be placed in a 14 day wash-out period, in both eyes, before they can be eligible. If in the discretion of the principle investigator, discontinuation of the topical treatment could pose any harm to the patient's ocular health, the patient will be excluded.
 - c. Patients who are on anti-histamines, oral (doxycycline or azithromycin) or topical antibiotics (bacitracin or erythromycin ointment) are eligible for as long as the doses have been stable in the past 2 weeks

- d. Patients who are on oral steroids or other anti-inflammatory or immunomodulatory medications are eligible for as long as the doses have been stable in the past 3 months
- e. Patients using glaucoma drops in either eye will be excluded (with the exception of rescue medication)

iii. Current systemic medications (see above)

iv. History of eye diseases and previous eye or eyelid surgery

- a. Patients who had eye surgery in the past 3 months prior to study are ineligible
- b. Patients who had penetrating corneal transplantation are not eligible

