This test involves placing a small piece of filter paper against the conjunctiva for 5 minutes to observe how much tear volume is being produced in the temporal part of the lower cul-de-sac. The filter paper is removed after 5 minutes, and the length of the paper wetted is measured to approximate tear production. The testing will be performed as minimally disturbing to the ocular surface as possible. Time will be recorded if Schirmer's are completely saturated prior to the 5 minutes.

7. Ocular surface staining (OSS).

- i. Corneal fluorescein staining: About 2.5 minutes after instillation of the fluorescein eye drops (one drop of saline placed on the commercially available fluorescein strips) the staining will be scored according to the criteria published by SICCA (11).
- ii. Conjunctival lissamine green staining: Within 1 minute after instillation of lissamine green eye drops (one drop of saline placed on the commercially available strips) the staining will be scored. Conjunctival staining will be measured based on SICCA criteria (11).

8. Dilated Fundus Examination (DFE)

1 drop of Tropicamide 1% and Phenylephrine 2.5% will be used in each eye for purpose of dilation. Macula, blood vessels and cup to disk ratio will be recorded.

9. Insertion of study drug.

Treatment eye will be randomized by a Randomization list made by the Biostat Center at Johns Hopkins School of Medicine (using REDcap database) contralateral eye of each patient will serve as the control

The Treatment Physician will place the study device and contralateral plug/sham treatment at Day 1. The Treatment or the Examining physician can do the baseline exam.

The Examining Physician will perform the study exams (Day 1 through 42) to preserve masking.

10. Unmasking procedures (Day 42 or for serious AE)

All tests require both eyes testing and will be performed in the right eyes first, then the left eyes.

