5.1.3 Adverse Event Information Collection

The investigator (or designee) will record all AEs that occur during the study.

The definition of an AE and SAE, and information on the determination of severity and relationship to treatment are provided in Section 7.

5.2 Safety and Rescue Criteria.

In the opinion of investigator, if the patient is at harm due to the treatment such as high eye IOP or due to control such as worsening of dry eye parameters, rescue medications can be used. To start IOP lowering medication, the IOP should be about 5 points higher than baseline. For additional dry eye medications/treatments the corneal staining should worsen a full severity grade.

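### IOP is measured before treatment but no eligibility rule uses it, and every numeric rescue trigger is relative, so untreated high pressure in both eyes is not screened out

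*Combined protocol and SAP*

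**What the plan says.** **Measurement.** Table 1 schedules IOP at run-in, Day 1, Days 14, 28 and 42, and early termination. The run-in is skipped for patients who do not need it, so for them Day 1 is the only reading before follow-up.

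**Eligibility.** Inclusion 8 in section 4.1.1 opens with "Presence of all of the following in both eyes at Baseline (Day 1" and then sets numeric limits for staining, Schirmer and VAS. IOP is not among them. Two exclusions in section 4.1.2 bear on pressure:
- Exclusion 5: "Use of topical glaucoma medications (With exception of rescue medication". Section 5.1, item 1.ii.e, repeats it: "Patients using glaucoma drops in either eye will be excluded (with the exception of rescue medication".
- Exclusion 12: "Known allergy or sensitivity to any of the clinical or experimental drugs used in this study including history of steroid response".

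Section 5.1, item 1.iv, takes a "History of eye diseases and previous eye or eyelid surgery", but its three sub-rules (a to c) deal only with surgery. For the dilated fundus examination (5.1, item 8), "Macula, blood vessels and cup to disk ratio will be recorded", with no entry limit attached.

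**Action after insertion.** The synopsis allows betaxolol, at the principal investigator's discretion, when IOP is "more than 5 points greater than baseline or more than 5 points higher than the fellow eye". Section 5.2 allows rescue more generally: "In the opinion of investigator, if the patient is at harm due to the treatment such as high eye IOP". It then says that IOP should be about 5 points over baseline before lowering medication is started. It does not mention the fellow eye. Section 5.1.2 foresees unscheduled visits for high IOP, without a number.

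**The concern.** Section 4.4 names raised eye pressure as a known steroid effect that can signal a vision-threatening disease, and offers IOP checks at every visit as the safeguard. A check protects the patient only if some value leads to action. Here the pre-treatment value leads to none, and later values count only as changes from that unscreened starting point.

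Both pressure exclusions depend on something already known: that the patient is on glaucoma drops, or has responded to steroids before. Neither catches high pressure first found at screening, or glaucoma that is not being treated with drops. Baseline may also follow steroid exposure, because patients on stable oral steroids, or off topical steroids for at least 2 weeks, are eligible. A trigger measured from baseline takes such a starting value as normal. The fellow-eye trigger does not help when both eyes start equally high.

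At stake is the safety of a probably small group of patients.

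**Working it through.** The plan gives no entry-pressure distribution and no figure to reproduce. The check is a reading of the rules followed by simple arithmetic on assumed pressures.

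**Step 1: is an absolute IOP value used anywhere?**

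| Place | What it uses |
|---|---|
| 4.1.1, inclusion 8 | staining, Schirmer, VAS; no IOP |
| 4.1.2, exclusion 5; 5.1, item 1.ii.e | current glaucoma drops |
| 4.1.2, exclusion 12 | known steroid response |
| 5.1, item 1.iv (a to c) | surgery only |
| 5.1, item 8 | cup-to-disk ratio recorded, no limit |
| Synopsis, rescue | change from baseline; difference from fellow eye |
| 5.2 | change from baseline; high IOP without a level |
| 5.1.2 | high IOP without a level |

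No absolute value appears in any of them.

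**Step 2: the rescue rules as formulas.** Let the treated eye start at T, let the sham eye start and stay at S, and let the treated eye later read I.
- Synopsis: triggered if I > T + 5 or I > S + 5.
- Section 5.2: triggered at about T + 5.

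**Step 3: symmetric high start, assumed T = S = 30.**
- Readings of 33, 34 and 33 on Days 14, 28 and 42 are rises of 3, 4 and 3 over baseline, and the same differences from the fellow eye. None exceeds 5, so the synopsis rule is not met. None reaches 5, so the 5.2 rule is not met unless its approximate wording is stretched to cover a rise of 4.
- A reading of 35 is a rise of exactly 5. The synopsis requires more than 5, so it is not met, but the 5.2 level is reached.

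**Step 4: asymmetric start, assumed T = 30, S = 27.** The synopsis fellow-eye rule acts above 27 + 5 = 32, while 5.2 acts at about 30 + 5 = 35. At 33 the difference from the fellow eye is 6 and the rise is 3, so the synopsis permits drops and the numeric rule in 5.2 does not.

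**Step 5: effect of an entry limit L.** Under the synopsis rule the highest reading that triggers nothing becomes at most L + 5. For L = 21 this is 26; for L = 24 it is 29. From an unscreened 30/30 it is 35. Adding an absolute level A that acts above A gives the smaller of L + 5 and A. With L = 24 and A = 27 that is min(29, 27) = 27. An A at or above L + 5 would add nothing.

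**The case against.** The strongest reply is that clinical judgement already covers the risk. These are patients in an eye clinic, judged to need an ocular steroid, with IOP, slit-lamp and fundus examination around entry. Known steroid responders are excluded. IOP is rechecked at every visit, unscheduled visits are foreseen, and 5.2 lets the investigator act on high pressure thought to be harmful. Harm needs a chain of events: untreated and roughly symmetric high pressure, no known steroid response, a clinician who sees the value and inserts anyway, a rise below about 5 points, and an investigator who then does nothing.

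Much of this stands, and it limits the weight of the point. It does not close the gap at entry. No criterion gives general discretion to decline a patient for high IOP; the one discretionary exclusion, in 5.1 item 1.ii.b, concerns harm from stopping topical treatment.

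A reader might infer that 5.2 forbids treating a rise of 3 or 4 points, or that its two sentences conflict. The text does not support that. The threshold is worded as a usual and approximate level, and it can be read together with the investigator's permission to act on harm. A reader might also infer that a full 5-point rise escapes every numeric rule. It escapes the synopsis rule but meets the one in 5.2.

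It is also fair to say that a further number that merely permits treatment would add little, since treatment is already permitted. The absolute level is useful only if it prompts an assessment.

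**Conclusion.** The point holds as a patient-safety gap that should be closed. Followed as written, the protocol admits a patient with untreated high IOP in both eyes to a steroid insert. A later rise of less than about 5 points from that baseline meets no numeric rule and rests on judgement without a stated level. The synopsis and 5.2 also differ, because only the synopsis has a fellow-eye trigger.

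The size cannot be estimated from the documents. All starting pressures above are assumptions, the sham eye is assumed unchanged, and the number of patients affected is unknown and probably small. The wording supports neither the inference that such patients would be left untreated nor any effect on the co-primary comparisons of staining and symptoms.

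**What to change.** 1. In 4.1.2, add an exclusion for pre-insertion IOP above a fixed limit in either eye. The investigators should choose the value and write it in; 21 to 24 is an illustrative range. State that the Day 1 reading used for this is taken before insertion, because the Day 1 list in 5.1.1 places insertion above IOP.
2. In 5.2, use the same relative rule as the synopsis, including the fellow-eye trigger.
3. As a secondary clarification, state in both places an absolute IOP level, below the entry limit + 5, at which the patient is to be assessed for pressure-lowering treatment whatever the change from baseline.

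The cost is a short protocol amendment. IOP is already scheduled at every visit, so no visit or procedure is added. The downside is a few screen failures and possibly a few more eyes given pressure-lowering drops.
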